11.2 Sample size

Phase II studies are usually small trials, recruiting participants up to about 20, although often a lot less. However, we plan to analyze the data stratified by different primary cancer such as breast, prostate, and etc., since we are trying to detect which patient subsets are most likely to benefit from the proposed treatment. The sample size can be set at approximately 10 for each patient subset in order to have a reasonable estimate of overall survival, local control, and quality of life for each subset. We estimate that most of the patients will have breast, lung, and prostate primaries and that there will be smaller numbers with other primary types. Based on these assumptions, we estimate a sample size of 40 patients and expect a 10% drop-out rate and thus have set an estimated sample size of 44 patients.

11.3 Data analysis

Two-year survival rate will be calculated for all the patients and each patient subset respectively by using Kaplan-Meier survival analyses, with survival and event times defined from the day of enrollment until either an event or last follow-up. We can compare these two year survival rates with those from the patients using traditional therapy. Median overall survival will also be estimated.

Univariate survival analysis will be performed to identify the statistically significant variables, using Log-Rank test or univariate Cox proportional hazard regression based on the data type of predictor variables. Significant ($P < .05$) variables on univariate analyses will then be tested with multivariate analyses by using Cox proportional hazard regression model (Milano MT, et al., 2007).

Quality of life outcomes will be analyzed by using univariate and multivariate logistic regression successively and the quality of life will be coded as "improved" or "non-improved".

We will also report the entire patient characteristics at initial presentation of oligometastatic disease and characteristics of Long-term (≥ 2 years) survivors by using descriptive statistics.

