HCC 10-027: Phase II study for Curative Intent Treatment for Patients with Oligometastatic Disease at Initial Presentation

Protocol version: 02/13/2023

Principal Investigator:

[name]- Assistant Professor
Department of Radiation Oncology
UPMC Presbyterian Shadyside
[contact]
Ph [contact]
[contact]

Statistician

[name]
UPMC Cancer Pavilion [name]
[name],
[name]
[contact]
Ph [contact]

NCT Number: NCT01345539

IND Number Exempt

Table of Contents

Summary	3
1.0 INTRODUCTION.....	4
2.0 OBJECTIVES.....	6
3.0 PATIENT SELECTION.....	6
4.0 PRETREATMENT EVALUATIONS/MANAGEMENT.....	8
5.0 TREATMENT OVERVIEW.....	9
6.0 RADIATION THERAPY.....	9
7.0 DRUG THERAPY.....	11
8.0 SURGERY.....	11
9.0 OTHER THERAPY.....	11
10.0 PATIENT ASSESSMENTS	12
11.0 STATISTICAL CONSIDERATIONS.....	13
12.0 DATA SAFETY AND RECORDING.....	14
REFERENCES.....	19
APPENDIX I - Schedule of events	22
APPENDIX II - Performance status scoring.....	23
APPENDIX III - Guidelines for SRS/SBRT dosing and fractionation	24
APPENDIX IV - Sample of QOL form (FACT-G)	27

Summary

Title: Phase II Study for Curative Intent Treatment for Patients Presenting with Oligometastatic Disease at Initial Presentation

Hypothesis: Patients with oligometastatic disease (defined here as 5 or fewer sites of metastatic disease involving 3 or fewer organ systems) are potentially curable with stereotactic radiosurgery (SRS) or stereotactic radiotherapy (SRT) (collectively referred to as stereotactic body radiotherapy or SBRT) to the metastatic disease sites in combination with standard curative therapy to the primary site.

[figure not shown]
Primary objective: Delivery of SBRT to multiple sites in a safe and effective manner with acceptable toxicity

Primary Endpoints:

- Presence of multiple sites (between 2 and 5 sites)
- Acceptable toxicity: Grade 3 or less

Secondary Objectives/Endpoints:

- Quality of life (as measured by the FACT quality of life surveys, see appendix IV)
- Local control of metastatic sites (with measurable/quantitative assessment): proportion of patients with Complete Response (CR), Partial Response (PR), or Stable Disease (SD)
- Local control of primary site (with measurable/quantitative assessment): proportion of patients with local Complete Response (CR), Partial Response (PR), or Stable Disease (SD)
- Overall survival (OS)
- Two-year Overall Survival

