2.0 OBJECTIVES

Primary objective: Delivery of SBRT to multiple sites in a safe and effective manner with acceptable toxicity

Primary Endpoints:

- Presence of multiple sites (between 2 and 5 sites)
- Acceptable toxicity: Grade 3 or less

Secondary Objectives/Endpoints:

- Quality of life (as measured by the FACT quality of life surveys, see appendix IV)
- Local control of metastatic sites (with measurable/quantitative assessment): proportion of patients with Complete Response (CR), Partial Response (PR), or Stable Disease (SD)
- Local control of primary site (with measurable/quantitative assessment): proportion of patients with local Complete Response (CR), Partial Response (PR), or Stable Disease (SD)
- Overall survival (OS)
- Two-year Overall Survival
- Analysis of patterns of failure post-SRS/SBRT (subsequent sites of failure and time to failure): proportion of patients with Progressive Disease (PD)

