10.3 Evaluation after study

10.3.1 Patients will be seen in follow-up with study physicians 6 weeks after completion of SRS/SBRT and then at 3 month intervals for 3 years and 6 months thereafter.

10.3.2 QOL survey to be performed prior to therapy, after SRS/SBRT and at subsequent follow-up visits using the FACT-G survey. See Appendix IV.

10.3.3 Toxicity will be evaluated after the study using Common Cancer Toxicity Criteria V 4.0

10.3.4 Follow-up imaging should be performed at least every 3 months for the first two years from completion of therapy and every 6 months afterwards until five years from the completion of therapy. FDG-PET/CT scan for follow-up is recommended but not required.

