11.0 STATISTICAL CONSIDERATIONS

Primary objective: Delivery of SBRT to multiple sites in a safe and effective manner with acceptable toxicity

Primary Endpoint(s):

- Presence of multiple sites (between 2 and 5 sites)
- Acceptable toxicity: Grade 3 or less

Secondary objectives/Endpoints:

- Quality of life (as measured by the FACT quality of life surveys, see appendix IV)
- Local control of metastatic sites
- Local control of primary site
- Overall survival (OS), Two-year Overall Survival
- Analysis of patterns of failure post-SRS/SBRT (subsequent sites of failure and time to failure)

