11.1 Objectives of the proposed study

The primary objective of the proposed phase II study is to evaluate the feasibility of this curative intent treatment approach (SRS/SBRT to the metastatic disease sites in combination with standard curative therapy to the primary site) to patients presenting with oligometastatic disease.

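### The hypothesis is cure, but the only time-to-event efficacy analysis clearly specified is overall survival with a two-year landmark, and no measure combines being alive with being progression-free

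*Combined protocol and SAP*

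**What the plan says.** The Summary states the hypothesis that patients with oligometastatic disease "are potentially curable with stereotactic radiosurgery (SRS) or stereotactic radiotherapy (SRT") given to the metastases, together with standard curative treatment of the primary.

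The primary objective in 11.0 is "Delivery of SBRT to multiple sites in a safe and effective manner with acceptable toxicity", with the endpoint "Acceptable toxicity: Grade 3 or less" beside a count of sites. Section 11.1 restates the aim as to "evaluate the feasibility of this curative intent treatment approach".

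Efficacy is secondary. The list in 11.0 includes "Overall survival (OS), Two-year Overall Survival", local control of the metastatic and primary sites, and failure. Section 2.0 words the last of these as "Analysis of patterns of failure post-SRS/SBRT (subsequent sites of failure and time to failure): proportion of patients with Progressive Disease (PD").

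For analysis, 11.3 says: "Two-year survival rate will be calculated for all the patients and each patient subset respectively by using Kaplan-Meier survival analyses". Times run from enrollment to an event, which is not defined, or to last follow-up. The section adds a median overall survival, log-rank and Cox screening of covariates, logistic regression for quality of life, and a description of patients who survive two years or more. It sets no disease-status condition on that last group.

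Under 10.3.4, imaging takes place at least every 3 months for two years and then "every 6 months afterwards until five years from the completion of therapy".

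**The concern.** Overall survival counts a patient as event-free whether or not the disease has come back. A patient can progress, which ends protocol treatment under 10.4, and still be described in 11.3 as a long-term survivor. Section 7.2 also allows systemic chemotherapy of the kind used for M1 disease after the primary has been treated, so survival at two years can reflect later treatment as well as the local approach.

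The endpoint nearest to a disease-free outcome, time to failure, is reduced to a crude proportion with progressive disease. With all patients in the denominator, someone who dies or is lost without documented progression counts as not having failed.

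What is at stake is how the results bear on the hypothesis. Section 11.2 wants to find the subsets that gain most from the treatment. A survivor profile that ignores progression may describe patients who live long with progressed disease rather than patients who stay free of it.

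**Working it through.** **1. The plan's own number.** Section 11.2 takes 40 patients and adds 10% for drop-out: 40 × 1.10 = 44, as stated. Dividing instead, 40 / 0.90 = 44.4, gives 45. The base of 40 reflects about 10 patients in each of about four subsets; no efficacy rate enters it. The point here does not affect it.

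**2. What the scans could support.** At the minimum schedule in 10.3.4, years 1–2 give 24 / 3 = 8 scans and years 3–5 give 36 / 6 = 6, a total of 14. The survival landmark is two years from enrollment, whereas the scan clock starts at completion of therapy. So at least the last 6 scans fall after the only named landmark.

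**3. Share of two-year survivors who have already progressed.** If OS₂ is two-year overall survival and PFS₂ is two-year progression-free survival, the share is 1 − PFS₂/OS₂. The documents give neither rate, so the inputs below are assumptions. Each cell shows the share and, in brackets, the number alive after progression out of 40, which is 40 × (OS₂ − PFS₂).

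| OS₂ | PFS₂ 10% | PFS₂ 20% | PFS₂ 30% | PFS₂ 40% |
|---|---|---|---|---|
| 40% | 75% (12) | 50% (8) | 25% (4) | – |
| 50% | 80% (16) | 60% (12) | 40% (8) | 20% (4) |
| 60% | 83% (20) | 67% (16) | 50% (12) | 33% (8) |
| 70% | 86% (24) | 71% (20) | 57% (16) | 43% (12) |

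The range is 20% to 86%. It is not a bound: if PFS₂ were close to OS₂, the share would be close to zero.

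**4. Can the planned summaries be combined to recover it?** Suppose, again as an assumption, that two-year overall survival is 60% and that 50% of patients have progressed by then. The proportion alive and progression-free is at most min(60%, 100% − 50%) = 50% and at least 60% + 50% − 100% = 10%. That is 4 to 20 of 40 patients from the same two reported figures, so they do not determine the quantity of interest.

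**5. Precision of the missing measure.** Exact (Clopper-Pearson) 95% intervals, treating every patient as fully followed:

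- 4 of 40 (10%): 2.8% to 23.7%
- 8 of 40 (20%): 9.1% to 35.6%
- 12 of 40 (30%): 16.6% to 46.5%
- 2 of 10 (20%, one subset): 2.5% to 55.6%

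Censoring would widen these.

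**6. Consistency of the progression rule.** Under the CT criteria in 10.3.5, a new lesion is progression. Under the PET criteria in 10.3.6, stable disease requires no new sites, but the definition of progression does not mention them. Section 10.4 applies the PET criteria to patients followed by PET, and 10.3.4 makes PET optional in follow-up. As written, a new site would be an event for one patient and not clearly so for another.

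**The case against.** The strongest reply is that this is a toxicity and feasibility trial. Two-year survival is one of several secondary endpoints, it has no threshold, and 11.3 describes the longer survivors without calling them successes. That is correct. A reader might infer that the trial's success is judged by two-year survival, or that it cannot answer its primary question; 11.0 and 11.1 support neither.

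A reader might also infer that the scans go unused. They do not: they feed both local-control endpoints, the sites of failure, the proportion with progression, and time to failure. The reference to event times in 11.3 could even be read as covering failure. What remains is that 11.3 does not define that event, say how death is handled, or name a method for it.

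Nor does all analysis stop at two years. Overall survival is listed apart from the two-year rate, and the median, log-rank and Cox analyses have no stated cut-off. The accurate statement is that no later landmark is named.

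It is also tempting to say that two-year survival is uninformative because breast and prostate cancers grow slowly. The documents do not say so, and 11.2 expects lung primaries as well. The plan's own evidence is enough: the Introduction argues for cure from five-year survival of 25–55% against 0–5% and from four-year survival of 59% against 0%, both longer than two years.

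Finally, two-year progression-free survival would not prove cure either, and within subsets it would be very imprecise. Both points stand. They argue for later time points and for estimation, not for leaving the measure out.

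**Conclusion.** The point holds as a gap in the secondary efficacy analysis. Overall survival with a two-year landmark is the only time-to-event efficacy analysis that 11.3 clearly specifies. Time to failure is listed but is neither defined nor analysed beyond a crude proportion, no measure joins survival with freedom from progression, and survivors are profiled without regard to disease status.

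The size of the effect is unknown. The 20% to 86% rests wholly on assumed rates (two-year overall survival 40–70%, progression-free survival 10–40%) and serves only to show that overall survival cannot stand in for disease-free status. It is the share who have ever progressed. Reading it as the share with active disease would go too far, since a progressed lesion may have been treated since.

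The primary endpoint, sample size and follow-up schedule are not in question here. The change is worth making because it is cheap and brings the efficacy analysis closer to the hypothesis.

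**What to change.** In 2.0 and 11.3:

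- Add progression-free survival as a secondary endpoint, from enrollment to the first of progression at any site or death from any cause, with a stated censoring date for patients without an event. Report it by Kaplan-Meier with 95% confidence intervals at 2 years, and at 3 and 5 years as data mature.
- State in one line that, for this endpoint, new lesions count as progression under both the CT and the PET criteria. This defines an analysis event; it does not touch the treatment rule in 10.4.
- Replace the crude proportion with progressive disease by the cumulative incidence of failure, with death as a competing event.
- Profile patients who are alive and progression-free at 2 years alongside all survivors at two years or more.
- Keep overall survival as planned.

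The cost is wording, one extra survival curve and one cumulative-incidence analysis from scans already scheduled, plus the agreed rule on new lesions. Progression-free survival cannot exceed overall survival, so the headline figure will be the same or, more likely, lower. Its intervals will be wide, especially within subsets, so it should be reported as an estimate without a test. No extra patients or scans are needed.

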The outcomes of patients treated with SBRT for multiple organ metastases have also been reported. The University of Rochester reported an analysis on 121 patients with 1-5 metastases treated on two consecutive protocols. Patients on both protocols could have had previous therapy for their disease; only 27 patients had oligometastatic disease at initial presentation. The first protocol treated breast cancer patients with limited metastases, in which no brain lesions were treated. The second protocol included patients with cancer from any primary site and limited metastases including a brain primary. After treatment with ten fractions of 5 Gy over 2 weeks (10 fractions), metastatic lesions were controlled 77% of the time at 2 years (25). Milano (5) reported prospective data on breast cancer patients with oligometastatic disease (less than 5 sites) comparing patients treated with SBRT to those receiving only palliative therapy. Four-year survival was significantly improved in SBRT patients (59% versus 0%). University of Chicago (53) reported on a prospective trial in 29 oligometastatic patients (one to five sites and a life expectancy > 3 months, 81% had prior systemic treatment) who had 56 metastatic lesions treated with SBRT (3 fractions ranging from a total dose of 24 to 36 Gy). The authors found a control rate of 56% for treated sites and only 2 patients had grade 3 or higher toxicity.

From the data available, patients with oligometastatic disease appear to benefit in terms of disease control from SBRT. At this point, no one is able to adequately predict which patients have favorable oligometastatic disease and are good candidates for aggressive and potentially curative therapy and which patients are destined to have development of widespread metastatic disease. Some proposed factors for patients likely to proceed to widespread metastatic disease include size and grade of primary tumor, site of oligometastatic disease, and lymph node status. In order to best treat patients, it is important that careful studies be performed to collect clinical information on patients with oligometastatic disease to analyze patient subsets most likely to benefit from treatment.

While disease outcome is certainly an important endpoint, quality of life (QOL) also is of significant importance, especially in patients with metastatic disease that have traditionally thought to

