be incurable. It is important that, until aggressive treatment for oligometastatic disease becomes standard of care, careful attention is paid to the quality of life in treated patients. Multiple validated QOL surveys are available for a variety of cancer sites. Collection of such surveys will help to monitor the impact of treatment on QOL.

To our knowledge, there have not been any prospective trials examining the role of aggressive therapy in the treatment of oligometastatic disease only at initial presentation. None of the previously described reports include only patients at initial presentation; the majority of patients in the prospective and retrospective oligometastatic studies have had previous therapy. In order to better evaluate the role of curative therapy in patients presenting with oligometastatic disease we are proposing a prospective study of this patient cohort. Patients with oligometastatic disease (defined for this study as 5 or fewer sites of disease involving 3 or fewer organ systems) will receive SRS/SBRT to all sites of oligometastatic disease and standard curative therapy to the primary disease. The primary objective for this study will be feasibility with the potential for an eventual phase III study. In addition, clinical and translational information will be collected to better stratify patients with oligometastatic disease for future studies.

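### Section 11.3 picks predictors by a one-at-a-time P<.05 screen and refits them on the same roughly 40 patients, so chance predictors with inflated hazard ratios are likely to be reported

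*Combined protocol and SAP*

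**What the plan says.** Section 11.3 sets out two steps for survival. First, "Univariate survival analysis will be performed to identify the statistically significant variables"; each is tested alone, by the log-rank test or a one-factor Cox model according to its type. Second, whatever reaches P<.05 goes forward: these "variables on univariate analyses will then be tested with multivariate analyses" in a Cox model. It lists no candidate variables, sets no maximum, makes no adjustment for the number tested, and includes no shrinkage or internal validation. It does not call the result exploratory.

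The Introduction (Section 1.0) mentions factors that have been proposed as markers of later widespread disease: "size and grade of primary tumor, site of oligometastatic disease, and lymph node status". That makes four, but they are given as background and not as the analysis list. Section 11.2 adds primary cancer type as the variable that defines the subsets. The Introduction also leaves the pool open, since "clinical and translational information will be collected to better stratify patients with oligometastatic disease for future studies".

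On size, Section 11.2 says "we estimate a sample size of 40 patients" and that the authors "expect a 10% drop-out rate", which gives 44 enrolled. No expected number of deaths is stated anywhere.

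**The concern.** Both steps use the same patients and the same deaths. A factor that enters the Cox model because its P-value was small by chance brings that chance result with it. If only one factor passes, the second model is the first one fitted again. The refit is therefore no independent confirmation. The P-values and confidence intervals that it prints take no account of the selection.

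A second effect concerns the size of the estimates. With few deaths, only a large observed hazard ratio can reach P<.05, so whatever passes the screen looks strong whether or not it is real.

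This matters because the protocol gives the factor search a purpose. Section 11.2 justifies the sample size by the wish to find the subsets that benefit most, and the Introduction wants the information to help stratify later studies and mentions a possible phase III trial.

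**Working it through.** **The plan's own figure.** The only stated number that bears on this analysis is the sample size: 40 × 1.10 = 44, as Section 11.2 says. (Dividing instead gives 40 / 0.90 = 44.4, a difference of no consequence here.) About 40 patients are available for analysis.

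**Inputs.** From the documents: a threshold of 0.05 per factor, unadjusted (Section 11.3; taken as two-sided, which is not stated), and 40 or 44 patients (Section 11.2). Assumed because the documents are silent: the number of candidate factors k, and the number of deaths d.

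**Step 1: chance that at least one unrelated factor passes the screen.** For independent factors this is 1 − 0.95^k.

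| k | Basis for k | 1 − 0.95^k |
|---|---|---|
| 4 | factors named in Section 1.0 | 1 − 0.8145 = 18.5% |
| 5 | those four plus primary cancer type | 22.6% |
| 10 | assumption | 40.1% |
| 15 | assumption | 53.7% |

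**Step 2: does the refit remove these?** The whole two-step procedure was simulated with every factor unrelated to survival.

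- Ten independent factors, 40 or 44 patients, 15, 20 or 30 deaths, 1,500 runs per setting (Monte Carlo standard error about 1.3 points): 40-45% of trials passed at least one factor at the screen, and 31-42% still had one at P<.05 in the refitted model (binary factors 31-40%, continuous 36-42%).
- About 27 deaths: a false predictor in the final model in 17% of trials with four factors, 24% with five and 40% with ten.
- Ten correlated factors: with latent correlation 0.3 to 0.5 and 20 deaths, 36-38% passed the screen and 26-31% remained after the refit. With correlation 0.4 and about 27 deaths, 31% remained.

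The refit therefore removes a modest share of the false findings, more when factors are correlated or deaths are few, and leaves most of them.

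**Step 3: size of the hazard ratios that get through.** For a balanced binary factor the standard error of the log hazard ratio is about 2/√d, so the smallest observed hazard ratio that reaches P<.05 is exp(1.96 × 2/√d). The right-hand column gives the simulated median, taken above 1, among retained factors whose true hazard ratio is 1.

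| Deaths d | Smallest significant hazard ratio | Median hazard ratio of falsely retained factors |
|---|---|---|
| 15 | exp(3.92/3.873) = 2.75 | about 3.7-3.8 |
| 20 | exp(3.92/4.472) = 2.40 | about 3.0 |
| 30 | exp(3.92/5.477) = 2.05 | about 2.4 |

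At about 27 deaths the simulated median was about 2.5. Real effects are exaggerated too: by the normal approximation, a true hazard ratio of 1.5 that passes the screen is reported at a median of about 2.4 with 30 deaths and 3.3 with 15. This part does not depend on k.

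**The case against.** The strongest reply is that the size of the problem rests on numbers the plan does not contain. Ten factors appear nowhere. A reader might take 40% to be the false-positive rate of this plan, and the documents do not support that. The factors they name number four, or five with primary cancer type, which roughly halves the figure. Size, grade and nodal status may well be correlated, which lowers it again. This part of the reply stands, and the result has to be given as a range. It does not remove the defect, because nothing holds the analyst to four or five factors, and even four give nearly one chance in five at the screen.

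A reader might also infer that the refit offers no protection at all. The simulations do not bear that out: it removes some false findings, though only a minority of them.

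A third reply is that the analysis is secondary. That is correct. The primary objective is feasibility and toxicity (Sections 2.0 and 11.1), finding prognostic factors is not among the listed secondary endpoints, and no stopping rule or phase III criterion uses the Cox result. It would go too far to say that the trial's main conclusion, its Kaplan-Meier rates or its median survival are compromised, or that a chance finding would necessarily shape the next trial. What remains is that Section 11.2 uses the search for subsets to justify the sample size, and the Introduction assigns the information to future stratification.

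Finally, penalization does not cure multiplicity. Firth's method corrects small-sample bias; three unadjusted 95% intervals on independent unrelated factors still give 1 − 0.95^3 = 14.3% that at least one excludes 1. Conventional intervals around ridge estimates are not straightforward either. The remedy must therefore rest on fixing the list and labelling the result, with Firth used only for stability.

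**Conclusion.** The concern holds in a limited form. Section 11.3 states a selection rule whose final P-values and intervals do not have their nominal meaning and whose hazard ratios are biased away from 1.

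If all factors are unrelated to survival, the chance of reporting at least one false predictor is about 17-19% for the four named factors, 23% for five and 40% for ten, with about 26-31% left after the refit if ten factors are moderately correlated. Falsely retained balanced binary factors show a median hazard ratio of about 2.4-2.6 at 27-30 deaths, and higher with fewer deaths. These sizes depend on the assumed number of factors, their correlation and the death count. The direction of the error does not.

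The plan should be changed, as a matter for a secondary analysis. The toxicity and feasibility endpoint is not affected.

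**What to change.** In Section 11.3, replace the univariate P<.05 screen with one Cox model specified before the outcome data are seen:

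- **Factors.** Fix a short list drawn from those the protocol names, and enter all of them whatever their univariate P. At 27-30 deaths, four single-coefficient factors would have about 7 deaths each (27/4 = 6.75; 30/4 = 7.5). The list should consider whether tumour size and grade mean the same thing across the primary sites in Section 3.1.2.
- **Primary cancer type.** Account for it in the model, for example in a few groups or as strata.
- **Estimation.** Use Firth penalization with profile-likelihood 95% confidence intervals, for small-sample stability.
- **Reporting.** State how many factors were examined, label the results hypothesis-generating, and describe any other factors without P-values.

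The cost is SAP wording; no extra patients, visits or data are needed. The downside is that fewer factors can be called significant. Stratifying by primary type also gives up direct hazard ratios between types.

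### The Cox and logistic models in 11.3 give no finite ratio or usable Wald interval for a small cancer subset with no deaths, or with all or none improved, and the plan has no rule for this

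*Combined protocol and SAP*

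**What the plan says.** Section 11.2 (Sample size) explains why the trial is larger than a usual phase II study: "we are trying to detect which patient subsets are most likely to benefit from the proposed treatment". It continues, "The sample size can be set at approximately 10 for each patient subset". Most patients are expected to have breast, lung or prostate primaries, and "there will be smaller numbers with other primary types". On this basis "we estimate a sample size of 40 patients and expect a 10% drop-out rate", which leads to 44.

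Section 11.3 (Data analysis) screens variables by log-rank test or univariate Cox regression at P < .05. Those that pass, as significant "variables on univariate analyses will then be tested with multivariate analyses by using Cox proportional hazard regression model", go to the second step. For the FACT-G outcome, coded improved or not improved, "Quality of life outcomes will be analyzed by using univariate and multivariate logistic regression successively".

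Section 11.3 does not list the predictors. It does not say whether P values come from Wald, score or likelihood-ratio tests. It has no provision for penalised or exact fitting, for a minimum number of events, or for a subset in which nobody or everybody has the event. Neither section gives an expected survival for any subset.

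**The concern.** Ordinary maximum likelihood has no finite solution when a category of a predictor contains no events. In a Cox model the partial likelihood keeps rising as the log hazard ratio for that category goes to minus infinity. The software stops at an arbitrary large negative value with an enormous standard error, and the Wald P drifts to 1. Logistic regression does the same when all or none of a category has the outcome.

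This matters because 11.2 wants to find the subsets that do best, and the subset with no deaths is the best result possible. The log-rank screen copes with that subset and may well pass primary cancer because of it. The Cox step then prints a hazard ratio of effectively zero with an unbounded interval. If the Wald P is the one read, it shows no difference on data where the log-rank test found one.

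**Working it through.** **The plan's own figure.** 40 × 1.10 = 44, as stated in 11.2 (40 / 0.90 = 44.4 would round up to 45). The sample size is not at issue here. The plan gives no power, effect size or event count to reproduce.

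**What the stated Cox model returns.** Constructed data: 40 patients, one subset of 10 with no deaths, and 30 others with 17 deaths by 24 months.

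| Method | Hazard ratio | Interval or SE | P |
|---|---|---|---|
| Log-rank | – | – | 0.004 |
| Ordinary Cox, Wald | 3e-9, still drifting | SE about 6,500 | 0.998 |
| Ordinary Cox, likelihood ratio | as above | – | 0.0003 |
| Firth Cox, penalised likelihood ratio | 0.060 | 95% profile 0.0005 to 0.44 | 0.0014 |

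With the same data in four groups and the zero-death subset as reference, the three other hazard ratios come out at about 2e8 to 5e8, each with Wald P 0.998. The global log-rank P is 0.013. With another subset as reference, only the zero-death coefficient fails.

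**The logistic model.** Constructed data: 0 of 10 improved against 12 of 30.
- Ordinary fit: coefficient −16 to −22 depending on the fitting routine, SE 1,154 to 15,241, Wald P 0.989 to 0.999.
- Ordinary likelihood ratio: the maximised log-likelihood is 12 ln 0.4 + 18 ln 0.6 = −20.19, and the null is 12 ln 0.3 + 28 ln 0.7 = −24.43. Twice the difference is 8.49 on 1 df, P = 0.0036.
- Firth: for a 2 × 2 table this adds one half to each cell, so OR = (0.5/10.5) / (12.5/18.5) = 0.070, with P = 0.014.

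**How often a subset has no deaths.** For n patients all followed to 2 years with 2-year survival S, the chance is S^n. The values of S are assumptions.

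| S | n = 10 | n = 3 | n = 2 |
|---|---|---|---|
| 60% | 0.6% | 22% | 36% |
| 80% | 11% | 51% | 64% |
| 90% | 35% | 73% | 81% |

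The one breast figure in section 1.0 is 59% survival at 4 years after SBRT. A constant hazard (assumed) makes that √0.59 = 77% at 2 years, so 0.59^5 = 7% for 10 patients and 0.59^1.5 = 45% for 3. By 4 years, 10 patients have a chance of 0.59^10 = 0.5%.

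**Effect of follow-up.** Take four subsets of 10 with assumed 2-year survival of 75, 50, 85 and 50% and constant hazards. The chance of at least one zero-death subset at 2 years is 1 − (1 − 0.75^10)(1 − 0.85^10)(1 − 0.50^10)² = 1 − 0.944 × 0.803 × 0.998 = 24%. With censoring spread evenly over 2 to 5 years it is 6.6%. With everyone followed 5 years (exponent 25 in place of 10) it is 1.8%.

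**Quality of life.** The chance that all or none of 10 improve is p^10 + (1−p)^10: 35%, 11%, 2.8% or 0.2% for p = 10, 20, 30 or 50%. For a subset of 2 it is p² + (1−p)², which is at least 50% for any p. For a single patient it is certain.

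**Does the factor reach the Cox step?** In simulations of four subsets of 10 whose true survival differed, the global log-rank P was below .05 in about 86 to 100% of the runs with a zero-death subset. So where this happens, primary cancer would usually pass the screen.

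**The case against.** A reader might infer that the multivariable conclusion for the best subset will be wrong. The documents do not support that, because 11.3 never specifies a Wald test. The likelihood-ratio test from the same ordinary Cox model keeps the signal. In simulations with assumed 2-year survival of 80/40/92/45%, it gave P < .05 for the zero-death subset in about 99% of the runs that passed a global screen (median P about 0.001). That figure is partly built in, since those runs were chosen for a significant global test. Even so, Firth fitting is not needed to recover significance. It is needed for a finite ratio and interval.

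A reader might also infer that a zero-death subset of 10 is to be expected. That requires assumed 2-year survival near 90% and follow-up cut off at 2 years. Section 11.3 counts survival time to last follow-up, section 10.3.1 schedules visits 3-monthly for 3 years and 6-monthly after that, and section 10.3.4 continues imaging to five years.

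Two further points stand. That primary cancer enters the models as a covariate is inferred from 11.2. If the stratification mentioned there means a stratified Cox model, a stratum with no deaths contributes nothing and no coefficient diverges. And the best subset is not hidden, since 11.3 also calls for a Kaplan-Meier 2-year rate in each subset, and no deaths would show there as 100%.

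What the objection does not remove is that the plan's models yield no usable ratio or interval for such a subset, and 11.3 does not say what is then to be reported.

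**Conclusion.** The point holds in a limited form. If primary cancer is a covariate, the stated Cox and logistic models give no finite ratio and no usable Wald interval for a subset with no deaths, or with all or none improved. The test result misleads only where Wald output is read.

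The likelihood depends on survival and improvement rates that the documents do not give. In subsets of 10 it runs from negligible (0.6% at 60% 2-year survival) to substantial (35% at 90%), and it shrinks as follow-up lengthens. It is most plausible for the other primaries: section 3.1.2 lists eight eligible disease groups, 11.2 expects most patients in three of them, and a group of two or three analysed separately can easily have no events.

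The affected models are secondary and exploratory. The primary objective (feasibility and toxicity) and the sample size of 44 do not depend on them. This is a minor improvement.

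**What to change.** In 11.3, state that the univariate and multivariable Cox models and the quality-of-life logistic models will be fitted by Firth penalised likelihood, with profile penalised-likelihood confidence intervals and penalised likelihood-ratio tests in place of Wald tests. Add that a subset with no deaths, or with all or none improved, stays in the model and is reported with its estimate and interval beside its event count and number of patients. In the same place, say whether primary cancer is a covariate or a stratification factor.

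This takes two or three sentences and a standard software option, with no extra patients or data. The downside is slight shrinkage of hazard and odds ratios toward 1. Intervals for sparse subsets will still be wide, because the method makes the estimate finite but adds no information.
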